Zwolle, The Netherlands

Protocol Synopsis

Title:	Fractional Flow Reserve guided Primary multivessel Percutaneous Coronary Intervention to improve guideline indexed actual standard of care for treatment of ST-elevation Myocardial Infarction in patients with multivessel disease.
Acronym:	Compare Acute : Comparison between FFR guided revascularization versus conventional strategy in acute STEMI patients with MVD.
Design:	Prospective, 1: 2 randomisation
Hypothesis:	FFR-guided complete percutaneous revascularisation of all flow-limiting stenoses in the non-IRA performed within the same procedure as the primary PCI or within the same hospitalisation will improve clinical outcomes compared to the staged revascularisation, guided by prove of ischemia or clinical judgment, as recommended from the guidelines.
Inclusion Criteria:	All STEMI patients between 18-85 years who will be treated with primary PCI in < 12 h (more than 12 hr if persisting pain allowed) after the onset of symptoms and have at least one stenosis of $\geq 50\%$ in a non-IRA judged feasible for treatment with PCI.
Key Exclusion Criteria:	Left main stem disease (stenosis > 50%) STEMI due to in-stent thrombosis Severe stenosis with TIMI flow \leq II of the non-IRA artery Non-IRA stenosis not amenable for PCI treatment Complicated IRA treatment Killip class III or IV already at presentation or at the end of culprit lesion treatment Intolerance to Aspirin, Clopidogrel, Prasugrel, Ticagrelor, Heparin, Bivalirudin, or Everolimus and known true anaphylaxis to prior contrast media or known bleeding diathesis or known coagulopathy Planned elective surgical procedure necessitating interruption of thienopyridines during the first 6 months post enrolment
Primary endpoint:	Composite endpoint of all cause mortality, non-fatal Myocardial Infarction, any Revascularisation and Stroke (MACCE) at 12 months
Major Secondary Endpoints:	Primary endpoint at 24 and 36 months as well as outcomes of each component of the primary endpoint at 12, 24 and 36 months. Primary endpoint rates at 12, 24 and 36 months in the subgroup of patients receiving staged or acute PCI treatment

for FFR positive lesions in the non-IRA vs the subgroup of patients that received optimal medical treatment though had a FFR positive lesion.

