In the FFR-guided complete revascularisation strategy group all flow limiting ($FFR \leq 0.80$) lesions will receive treatment by PCI and stenting. The non-IRA PCI should be performed during the same intervention. Exceptions can be made for complex lesions where the operator estimates that the revascularisation procedure will require significant contrast overload which may lead to deterioration of cardiac and renal function of the patient. Such procedures can be performed in a second procedure which should take place within the same hospitalisation, preferably within 72 hours.

All lesions with a FFR measurement of >0.80 will not be treated.

In the randomised to guidelines group the procedure will stop after the FFR measurements and the patient will be referred to his treating cardiologist who will decide whether a staged PCI of the non-IRA artery should take place. The treating cardiologist will be blinded for the FFR measurements (but not angiographic imaging) and must make a decision based on conventional non-invasive ischemia detecting tests or clinical signs and symptoms i.e. very typical angina symptoms in patients with angiographic significant stenosis. After the PPCI procedure the FFR values will not be reported in the conventional PCI report but will be registered in the study database only. If the treating cardiologist decides to perform the non-IRA PCI revascularisation, than such treatment should take place within six weeks (45) days from the primary PCI in order to count as a scheduled staged PCI procedure. Any other revascularizations of any lesions after these 6 weeks are identified as unscheduled and therefore counted as an event. Per definition the treating cardiologist should be a different person from the operator.

All revascularisations procedures will be defined as clinically indicated or not clinically indicated by the independent clinical event committee. Non clinically indicated revascularisation will be counted as an event.

Blinding for the FFR results is required to perfectly mimic the standard care treatment in the randomised to guidelines group and avoid bias in further decision tree.

Blinding for the FRR results in this group allows for the following subgroup (shown in figure 2) comparisons and will try to give answers to following dilemmas in the treatment of STEMI patients presenting with multivessel disease:

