- 1) Clinical outcomes differences between PCI treatment vs optimal medical treatment in patients with at least one FFR positive lesion (group c vs group d)
- 2) Staged PCI versus acute (during PPCI) revascularisation of FFR positive lesions (group a vs group c)
- 3) Optimal Medical Treatment versus PCI treatment of FFR negative lesions (group b + f vs group e)

In order to balance the number of patients in these subgroups we chose for a 1:2 randomisation pattern.

[figure not shown]

Figure 2: Subgroups resulting from this randomisation.

Endpoints

Primary endpoint:

Composite endpoint of all cause mortality non-fatal Myocardial Infarction, any Revascularisation and Cerebrovascular Events (MACCE) at 12 months between groups (a+b versus c-f).

Secondary endpoints:

1. Primary endpoint at 24 and 36 months as well as outcomes of each component of the primary endpoint at 12, 24 and 36 months.
2. Primary endpoint rates at 12, 24 and 36 months in the subgroup of patients receiving staged or acute PCI treatment for FFR positive lesions in the non-IRA vs the subgroup of patients with FFR positive lesion that received optimal medical treatment. {figure 2, subgroups (a+c) vs subgroup d}
3. Primary endpoint rates at 12, 24 and 36 months in the subgroup of patients receiving acute PCI treatment for FFR positive lesions in the non-IRA vs the subgroup of patients receiving staged PCI treatment for FFR positive lesions in the non-IRA (figure 2 subgroups a vs c)
4. Primary endpoint rates at 12, 24 and 36 months in the subgroup of patients receiving staged PCI treatment for FFR negative lesions in the non-IRA vs the subgroup of patients not receiving PCI treatment for FFR negative lesions in the non-IRA. (figure 2 subgroups e vs b+ f)
5. Composite endpoint of Cardiac death, Myocardial Infarction, any Revascularisation, Stroke and Major bleeding at 12, 24 and 36 months (NACE i.e. Net Adverse Clinical Events)
6. A composite of hospitalisation for heart failure and unstable angina pectoris at 12, 24, and 36 months
7. All cause mortality or Myocardial infarction at 12, 24 and 36 months

8. Any revascularisation at 12, 24 and 36 months
9. Stent thrombosis at 12 months, 24 and 36 months
10. Bleeding at 48 hr and 12 months.
11. Treatment costs 12 months, 24 and 36 months

Definitions

Death

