In the guideline guided group the staged non-IRA revascularisations can take place until day 45 post primary PCI. These will be called **staged non-IRA revascularisations** and will not be counted as an event revascularisation, unless the Clinical Event Committee considers these revascularisations as clinically not justifiable.

All urgent revascularisations (in both strategy arms) will be counted as events. All other revascularisations that do not qualify as **delayed** or **staged non-IRA revascularisations** will be counted as events. All revascularisations that will take place beyond the 45 days will also be counted as event revascularisations.

Clinically indicated:

A revascularization is clinically indicated if angiography shows a percent diameter stenosis $\geq 50\%$ (QCA) **and** if one of the following occurs:

- 1) A positive history of recurrent angina pectoris presumably related to the target vessel.
- 2) Objective signs of ischemia at rest (ECG changes) or during exercise test (or equivalent) presumably related to the target vessel.
- 3) Abnormal results of any invasive functional diagnostic test (e.g. Doppler flow velocity reserve, fractional flow reserve). The results of the test must be documented in the Case Report Form.

Not Clinically indicated are re-interventions for:

1. all stenoses in absence of ischemic signs or symptoms.

Stent Thrombosis

We follow the ARC definitions³⁰. Stent Thrombosis should be reported as a cumulative value at the different time points and with the different separate time points. Time 0 is defined as the time point after the guiding catheter has been removed and the patient left the Cathlab.

Timing

Acute stent thrombosis(*):	0 – 24 hours post stent implantation
Subacute stent thrombosis(*):	>24 hours – 30 days post stent implantation
Late stent thrombosis:	>30 days – 1 year post stent implantation
Very late stent thrombosis:	>1 year post stent implantation

(*) acute/subacute can also be replaced by early stent thrombosis. Early stent thrombosis (0 – 30 days) – this definition is currently used in the community.

We recognize three categories of evidence in defining stent thrombosis:

- 1) Definite
- 2) Probable
- 3) Possible

1) Definite* stent thrombosis

Angiographic confirmation of stent thrombosis†

The presence of a thrombus that originates in the stent or in the segment 5 mm proximal or distal to the stent and presence of at least 1 of the following criteria within a 48-hour time window:

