if at the time of hospital discharge he or she had a moderate deficit (substantial limitation of activity and capabilities) or a severe deficit (inability to live independently or work). Modified Rankin scale grade of > 4 (see below)

Modified Rankin Scale - Stroke severity assessment scale

Scale 0

No symptoms at all

Scale 1

No significant disability despite symptoms: able to carry out all usual duties and activities

Scale 2

Slight disability: unable to carry out all previous activities but able to look after own affairs without assistance

Scale 3

Moderate disability: requiring some help, but able to walk without assistance

Scale 4

Moderately severe disability: unable to walk without assistance, and unable to attend to own bodily needs without assistance

Scale 5

Severe disability: bedridden incontinent and requiring constant nursing care and attention

Urgent Revascularisation

Any PCI or bypass surgery for recurrent ischemia that in the investigators opinion can not be delayed for more than 24 hours and is defined by the investigator as a non-elective procedure.

Target Lesion revascularisation

TLR is defined as any ischemia-driven repeat PCI of the target lesion or bypass surgery of the target vessel. Target lesion is defined as the vessel segment composed by the treated segment including the adjacent 5mm distal and proximal to the treated segment.

Target Vessel revascularisation

TVR as any ischemia-driven repeat PCI or bypass surgery in any lesion of the target vessel. The target vessel is one of the 3 main epicardial coronary artery or bypass graft that contains the target lesion.

NYHA Classification of Heart Failure

Class I

No limitation of activities; patients suffer no symptoms from ordinary activities.

Class II

Slight, mild limitation of activity; patients are comfortable with rest or with mild exertion.

Class III

Marked limitation of activity; patients are comfortable only at rest.

Class IV

Patients who should be at complete rest, confined to bed or chair; any physical activity brings on

Killip Classification of Heart Failure

Class I

The absence of rales over the lung fields and the absence of an S3.

Class II

The presence of rales, that do not clear with coughing, over one half or less of the lung fields or the presence of an S3.

Class III

The presence of rales that do not clear with coughing, over more than half the lung fields.

Class IV

Cardiogenic shock

Cardiogenic Shock

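### Secondary endpoints 2 to 4 split the guideline arm by staged PCI received up to day 45, so as written they are non-randomised and open to immortal-time and indication bias; the by-arm contrasts within FFR stratum are not listed

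*Combined protocol and SAP*

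**What the plan says.** **The contrasts.** Under Endpoints, secondary endpoint 2 compares rates "in the subgroup of patients receiving staged or acute PCI treatment for FFR positive lesions in the non-IRA vs the subgroup of patients with" an FFR-positive lesion treated medically, written as (a+c) vs d. Endpoint 3 is a vs c and endpoint 4 is e vs (b+f). The Protocol Synopsis lists all three as major secondary endpoints and describes group d as "the subgroup of patients that received optimal medical treatment though had a FFR positive lesion". The Trial design description puts the first question differently: "Clinical outcomes differences between PCI treatment vs optimal medical treatment in patients with at least one FFR positive lesion (group c vs group d").

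**How the groups form.** In the guideline arm the treating cardiologist, blinded to FFR, "must make a decision based on conventional non-invasive ischemia detecting tests or clinical signs and symptoms". If PCI is chosen, "such treatment should take place within six weeks (45) days from the primary PCI in order to count as a scheduled staged PCI procedure".

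**What counts as an event.** The Revascularisation definition says "All urgent revascularisations (in both strategy arms) will be counted as events", and an urgent procedure "is defined by the investigator as a non-elective procedure". A staged PCI does not count unless the event committee finds it clinically unjustifiable; then it does.

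**Why 1:2.** The Trial design description says: "In order to balance the number of patients in these subgroups we chose for a 1:2 randomisation pattern".

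**Analysis.** Statistical Considerations names chi-square or Fisher tests, Wilcoxon tests and Kaplan-Meier curves. FFR is to be measured in every patient of both arms, after randomisation.

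**The concern.** Groups c and d, and likewise e and f, separate after randomisation. To enter c or e a patient must reach the staged PCI alive and still suitable for it. If a control patient who dies or needs urgent revascularisation first falls into d or f, early events move into the no-PCI group whether or not PCI has any effect. That is immortal-time bias. Selection on ischaemia or symptoms adds indication bias, which blinding to FFR does not remove. Nothing in the named methods deals with either.

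The visible text gives no time origin for these contrasts and no group for a control patient with an event before staged PCI. It does not list the two comparisons that randomisation could support within FFR strata: a vs (c+d) and b vs (e+f).

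These contrasts are meant to answer whether PCI beats medical treatment for FFR-positive lesions, whether acute beats staged PCI, and whether PCI of FFR-negative lesions helps or harms. They are also the stated reason for unequal allocation.

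**Working it through.** **1. The plan's sample size and the price of 1:2.** Inputs from Statistical Considerations: 8% vs 14.5%, two-sided 5%, 80% power, pooled normal approximation. With k controls per FFR-guided patient,

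n1 = [1.96·√(p̄(1−p̄)(1+1/k)) + 0.8416·√(p1(1−p1) + p2(1−p2)/k)]² / (p2−p1)².

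- k = 2: p̄ = 0.1233; (0.7893 + 0.3099)²/0.004225 = 285.98, so 286 + 572 = 858. Then 858/0.97 gives 885. The plan's figures reproduce.
- k = 1: p̄ = 0.1125; (0.8758 + 0.3741)²/0.004225 = 369.8, so 370 + 370 = 740.

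The 1:2 ratio costs 858 − 740 = 118 patients before loss to follow-up.

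**2. Expected group sizes (295/590).** The plan assumes a 50:50 FFR split in the guideline arm, with PCI chosen in 70% of FFR-positive and 50% of FFR-negative patients. I assume the same split in the FFR-guided arm. Then a = b = 147.5, c+d = e+f = 295, intended c = 206.5, intended d = 88.5, intended e = f = 147.5.

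**3. Immortal time alone, no true effect.** The documents give none of these inputs, so all are assumed: 12-month risk r = 10%; share s of events before day 45, 12–40%; early events uniform on days 0–45; planned PCI uniform on days 2–45, so that 23.5/45 = 0.522 of early events precede it; probability q that such an event precludes the PCI, 10–100%. The fraction of intended-PCI patients moved is m = r·s·0.522·q. Then:

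- rate in c or e = (r−m)/(1−m)
- rate in d = (0.3r+0.7m)/(0.3+0.7m)
- rate in f = (r+m)/(1+m)

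| s, q | m | c or e | d | (a+c)/d | a/c | e/(b+f) |
|---|---|---|---|---|---|---|
| 12%, 10% | 0.0006 | 9.94% | 10.13% | 0.98 | 1.01 | 0.99 |
| 20%, 50% | 0.0052 | 9.53% | 11.08% | 0.88 | 1.05 | 0.93 |
| 40%, 100% | 0.0209 | 8.08% | 14.18% | 0.63 | 1.24 | 0.74 |

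Last row, (a+c): (14.75 + 16.34)/(147.5 + 202.19) = 8.89%, and 8.89/14.18 = 0.63. Event rates of 8–20% move the limits by at most 0.04.

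**4. The committee rule pulls the other way.** Only c and e can have a staged PCI ruled unjustifiable. If a share u of e's staged PCIs is so ruled, e's rate x becomes x + u(1−x). The e/(b+f) ratio returns to 1 when u = (rate in b+f − x)/(1−x):

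- middle row: (10.23 − 9.53)/(100 − 9.53) = 0.8%
- last row: (10.93 − 8.08)/(100 − 8.08) = 3.1%

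At an assumed u of 5% the ratios become 1.37 and 1.16.

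**5. The missing early-event rule (illustration).** Take s = 20%, half of the early events before the planned PCI being urgent PCI, and 20% preclusion for the rest. Then m = 0.01044 × (0.5 + 0.5 × 0.2) = 0.0063, (a+c) is 9.67% and d is 11.30%, a ratio of 0.86. If controls with an event by day 45 and no staged PCI are left out instead, d is 0.08/0.98 = 8.16% and the ratio is 1.18.

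**6. By-arm contrasts.** Power = Φ[(|p2−p1| − 1.96·SE0)/SE1] at 147.5 vs 295, with SE0 the pooled and SE1 the unpooled standard error.

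- a vs (c+d), 8% vs 14.5%: (0.0650 − 0.0650)/0.0303 ≈ 0, power 50%. At 8% vs 20%: (0.12 − 0.0725)/0.0323 = 1.47, power 93%.
- b vs (e+f), 8% vs 11%: (0.03 − 0.0593)/0.0288 = −1.02, power 15%.
- Half-width of the 95% CI for a vs (c+d): 1.96 × 0.0303 ≈ 6 points.

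Stratum rates are assumed. One set that averages to the plan's 14.5% is a base of 8.5%, 5 points more after staged PCI and the plan's 20 points more in d: c+d = 8.5 + 0.7×5 + 0.3×20 = 18%, and e+f = 8.5 + 0.5×5 = 11%.

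**7. Do standard remedies work?** In a null simulation of c vs d, a day-45 landmark gave ratios of 0.99–1.01 and a time-dependent exposure 0.99–1.01, against naive ratios of 0.57–0.99. Only c vs d was simulated.

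**The case against.** The strongest reply is that the plan calls these subgroup comparisons, attaches no alpha to them, and writes its methods generically, so the analysis of groups a to f is unspecified rather than wrong. Some rules also exist: staged PCI is scheduled and falls within 45 days, and urgent PCI is non-elective, which favours reading it as not staged. This stands in part. But the Synopsis ranks these as major secondary endpoints, the Assumptions section says the trial will prove each of its assumptions, and applying the named methods to the listed groups gives the biased comparison.

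The ratio ranges rest on assumed inputs and run from almost nothing to extreme. That stands, and they are illustrations only.

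The added contrasts compare strategies. They isolate neither PCI from medical treatment nor acute from staged PCI, and b vs (e+f) has little power. That also stands, so they supplement the listed questions.

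Endpoint 3 words group a by acute PCI received, and Figure 2 is not shown. If a means PCI received, a vs (c+d) is not a by-arm contrast. This stands and shapes the fix.

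A reader might infer that endpoints 2 and 4 must flatter PCI. The documents do not support this: symptom-driven selection and the committee rule can both work against c and e. Nor do they support any doubt about the primary result, since a+b vs c–f follows randomised arm.

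**Conclusion.** The point holds for secondary endpoints 2 to 4. As written they are non-randomised contrasts open to immortal-time and indication bias, and the named methods address neither.

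Under the assumed inputs and no true effect, immortal time alone gives (a+c)/d between 0.63 and 0.98, with 0.88 in the middle case. The extreme needs every early event before the planned PCI to preclude it. For e/(b+f), having about 1–3% of staged PCIs ruled unjustifiable would cancel the middle-to-extreme bias, and more would reverse it. Net size and direction are therefore unknown.

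The 118 extra patients are the cost of 1:2 against 1:1 at equal power. It would go too far to call them wasted: they still contribute to the primary comparison and to the by-arm contrasts proposed here.

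Figure 2 may define the groups further. The weight is that of a change that should be made, not of a threat to the trial's main conclusion.

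**What to change.** 1. **Add a vs (c+d) and b vs (e+f)** as by-arm estimates with 95% CIs and an arm-by-FFR interaction. Define the strata by randomised arm and measured FFR (at least one non-IRA lesion at or below the protocol's 0.80, or none), not by PCI received. Report missing FFR by arm, because FFR is measured after randomisation. State that these compare strategies and are not confirmatory.
2. **Keep endpoints 2 to 4, labelled non-randomised and exploratory.** State the time origin, and the analysis group of a control patient who dies, has a non-fatal event or has an urgent PCI before a staged PCI. For the PCI vs no-PCI contrasts, treat staged PCI as a time-dependent exposure or use a day-45 landmark. Report them with and without events that consist only of a staged PCI judged unjustifiable. Report a vs c as descriptive only, since neither method has been worked out for it.
3. **Reconcile** c vs d in the design list with (a+c) vs d in endpoint 2.

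The cost is a wording amendment and a little more analysis. FFR values are already to go into the study database, and the 45-day rule already needs PCI dates. The drawbacks are that the added contrasts are imprecise (about ±6 points) and could be weakened by unequal missing FFR, a landmark drops the events before day 45, and indication bias remains in the listed contrasts.

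### In secondary endpoints 2–4, and chiefly endpoint 4, a staged PCI that the committee rules against both assigns the control patient to a PCI group and counts as that patient's event

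*Combined protocol and SAP*

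**What the plan says.** All references are to the combined protocol and SAP.

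**The groups.** Under Endpoints, the primary comparison is randomised, with an outcome that includes "any Revascularisation and Cerebrovascular Events (MACCE) at 12 months between groups (a+b versus c-f"). Secondary endpoints 2–4 apply the same outcome to groups formed by FFR result and treatment received:

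- Endpoint 2 sets PCI-treated FFR-positive patients against those "with FFR positive lesion that received optimal medical treatment. {figure 2, subgroups (a+c) vs subgroup d".
- Endpoint 3 compares acute with staged PCI ("figure 2 subgroups a vs c").
- Endpoint 4 takes "Primary endpoint rates at 12, 24 and 36 months in the subgroup of patients receiving staged PCI treatment for FFR negative lesions" and compares it with no PCI of such lesions (e versus b+f).

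Groups c and e are therefore control patients who had staged PCI, and d and f are control patients who did not.

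**The event rule.** Under Definitions, Revascularisation, in the guideline arm "the staged non-IRA revascularisations can take place until day 45 post primary PCI". These procedures "will not be counted as an event revascularisation, unless the Clinical Event Committee considers these revascularisations as clinically not justifiable". The Trial design description has the committee classify every revascularisation and adds: "Non clinically indicated revascularisation will be counted as an event".

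**The indication criterion.** The same Definitions section treats a revascularisation as clinically indicated when QCA stenosis is at least 50% and there is recurrent angina, objective ischaemia, or an abnormal invasive functional test. FFR is named as one such test.

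The text gives no separate event definition for endpoints 2–4, and no rule that leaves out the procedure defining the group.

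**The concern.** In the randomised comparison, counting an unjustified staged PCI is defensible: the protocol regards a procedure outside the planned strategy as a failure of that strategy, and group membership does not depend on it. In endpoints 2–4 PCI is the exposure. If the committee rules against a staged PCI, that patient is in c or e because of the procedure and has an event because of the same procedure. A control patient in d or f has no staged PCI to be judged.

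This is distinct from confounding by indication and from immortal time. It would remain if the groups were perfectly comparable, because a judgement on the appropriateness of the PCI is added to the event rate of the PCI group.

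Endpoint 4 has most at stake. It is meant to show whether treating FFR-negative lesions helps or harms, and it could show harm when PCI has no effect on death, infarction, stroke or later revascularisation.

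**Working it through.** **The plan's own figure.** Pooled-variance chi-square, 8% versus 14.5%, 1:2 allocation, two-sided 5%, 80% power.

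- Mean rate = (0.08 + 2 × 0.145)/3 = 0.1233.
- n(FFR) = [1.960 × √(1.5 × 0.1233 × 0.8767) + 0.842 × √(0.08 × 0.92 + 0.145 × 0.855/2)]² / 0.065² = 286.
- Control 572, total 858. Allowing for 3% loss, 858/0.97 = 885.

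Both totals match Statistical Considerations. No figure is stated for endpoints 2–4.

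**Expected group sizes.** Statistical Considerations gives 295/590 randomised, an equal FFR split, PCI in 70% of FFR-positive controls, and no PCI in 50% of FFR-negative controls.

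- a = b = 295 × 0.5 = 147.5
- c = 590 × 0.5 × 0.7 = 206.5; d = 590 × 0.5 × 0.3 = 88.5
- e = f = 590 × 0.5 × 0.5 = 147.5; so b+f = 295

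**Null model (assumed).** PCI has no effect and every group has the same true rate p0. A share u of staged PCIs is ruled against, independently of other events. The documents do not give u, so a range is used.

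- Scored rate in the staged group = p0 + (1 − p0)u.
- Chance of a significant chi-square = Φ[(δ − 1.96·s0)/s1] + Φ[(−δ − 1.96·s0)/s1], where δ is the difference in scored rates, s0 the pooled standard error and s1 the unpooled one.

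**Worked case: endpoint 4, p0 = 8%, u = 5%.**

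- Rate in e = 0.08 + 0.92 × 0.05 = 0.126, against 0.080 in b+f; δ = 0.046.
- Pooled rate 0.0953, s0 = 0.0296, s1 = 0.0316.
- (0.046 − 1.96 × 0.0296)/0.0316 = −0.38, so the chance is about 35%.
- Extra events in e = 147.5 × 0.046 = 6.8.

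**Endpoint 4 over the range.**

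| u | Rate in e (p0 = 8%) | Falsely significant | Rate in e (p0 = 14.5%) | Falsely significant |
|---|---|---|---|---|
| 0 | 8.0% | 5% | 14.5% | 5% |
| 2% | 9.8% | 11% | 16.2% | 8% |
| 5% | 12.6% | 35% | 18.8% | 22% |
| 10% | 17.2% | 80% | 23.1% | 60% |

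Simulation of 200,000 trials per cell agrees: significant results against staged PCI in 10.4%, 35.0% and 81.2% at p0 = 8%, and 7.4%, 22.2% and 60.8% at p0 = 14.5%.

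**Endpoints 3 and 2.** If c had the same u as e, with p0 = 8%, endpoint 3 would be falsely significant in about 27% (u = 5%) and 72% (u = 10%). These are upper bounds, because c is FFR-positive and any such lesion with QCA stenosis of at least 50% already meets the indication criterion. Endpoint 2 is also diluted by group a. At u = 5% the a+c rate is (147.5 × 0.08 + 206.5 × 0.126)/354 = 10.7%, with about 10% falsely significant; at u = 10% about 25%. These too are upper bounds.

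**The case against.** **Protocol-compliant staged PCI should mostly pass review.** The treating cardiologist must decide on ischaemia tests or typical symptoms, which closely match the first two indication criteria. This stands as a reason why u may be small, and at u = 2% the endpoint 4 figure is only about 11%. It does not make u zero. Entry allows visual estimation, while the indication criterion needs QCA of at least 50%. The plan also expects half of FFR-negative controls to have PCI.

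**Group c is largely protected.** This stands. A reader might infer that endpoints 2, 3 and 4 are equally affected. The documents do not support that: c is exposed only where QCA is below 50% or the committee does not use the FFR value. FFR is hidden from the treating cardiologist but held in the study database, and the text does not say whether the committee uses it.

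**Group b has its own rule.** This stands in part. Group b belongs to the FFR arm, so its patients cannot move to c or e. A reintervention there that does not qualify as a delayed procedure counts as an event, whereas a justified staged PCI before day 45 in the control arm does not. That can offset some of the excess in endpoint 4. It is not circular, because the procedure does not define membership of b.

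**Benefit of PCI over medical treatment would be hidden.** A reader might infer this for endpoint 2, but the plan's figures do not support it. Statistical Considerations expects 20% on top of standard rates in medically treated FFR-positive patients. Taking 8% as the standard rate (an assumption), d is about 28%. Even at u = 10% applied fully to c, a+c is 13.4% and the benefit is detected with about 88% power.

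**Early urgent PCI.** A reader might also infer the same circularity here, since "All urgent revascularisations (in both strategy arms) will be counted as events". The documents treat urgent procedures separately from scheduled staged PCI and do not say that an urgent procedure assigns a patient to c or e. Figure 2 was not visible in the text reviewed. Charging every early urgent PCI to d or f without a landmark would add a bias of its own, so no such rule is proposed.

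**These comparisons are non-randomised and secondary.** True, and other biases act the opposite way: a patient must survive to staged PCI to enter c or e, and any PCI after day 45 in d or f counts as an event. This limits what can be said about net direction, but it is no reason to keep a known artefact that is easily removed.

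**Conclusion.** The point holds, mainly for endpoint 4. As written, a staged PCI ruled not justifiable or not clinically indicated is both exposure and outcome, and nothing in the text removes it from endpoints 2–4.

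With a common true rate of 8% and the planned group sizes, the false-significance rate in endpoint 4 is about 11%, 35% and 80% at u = 2%, 5% and 10%. With a 14.5% background it is about 8%, 22% and 60%. The nominal level is 5%. The size rests wholly on u, which the documents do not give; at u = 0 this route adds nothing.

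Endpoints 3 and 2 are exposed only through the limited part of c described above, and endpoint 2 is diluted further. The documents do not support a claim that the net result must be biased against PCI. The randomised primary comparison and the sample size are unaffected.

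**What to change.** Add to secondary endpoints 2–4:

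> The staged PCI that assigns a patient to group c or e is not counted as an event in these comparisons. Deaths, myocardial infarctions, strokes and all other revascularisations count as in the primary endpoint.

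Leave the event rule for the primary comparison (a+b versus c–f) unchanged. With the assigning procedure left out, u is in effect zero and the null risk ratio from this route returns to 1.00 in all three endpoints.

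The cost is two sentences, with no new data and no change in sample size. The small downside is that the revascularisation count in these secondary comparisons will differ slightly from that in the primary endpoint, which a table footnote can explain. The change does not address the other biases of comparing groups by treatment received.
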